Pregabalin treatment was associated with creatine kinase elevations. Mean changes in creatine kinase from baseline to the maximum value were 60 U/L for pregabalin-treated patients and 28 U/L for the placebo patients. In all controlled trials across multiple patient populations, 1.5% of patients on pregabalin and 0.7% of placebo patients had a value of creatine kinase at least three times the upper limit of normal. Three pregabalin treated subjects had events reported as rhabdomyolysis in premarketing clinical trials. The relationship between these myopathy events and pregabalin is not completely understood because the cases had documented factors that may have caused or contributed to these events. Instruct patients to promptly report unexplained muscle pain, tenderness, or weakness, particularly if these muscle symptoms are accompanied by malaise or fever. Discontinue treatment with pregabalin if myopathy is diagnosed or suspected or if markedly elevated creatine kinase levels occur.

12. **Decreased Platelet Count**

Pregabalin treatment was associated with a decrease in platelet count. Pregabalin-treated subjects experienced a mean maximal decrease in platelet count of $20 \times 103/\mu$ L, compared to $11 \times 103/\mu$ L in placebo patients. In the overall database of controlled trials, 2% of placebo patients and 3% of pregabalin patients experienced a potentially clinically significant decrease in platelets, defined as 20% below baseline value and $<150 \times 103/\mu$ L. A single pregabalin treated subject developed severe thrombocytopenia with a platelet count less than 20 x 103/ uL. In randomized controlled trials, pregabalin was not associated with an increase in bleeding-related adverse reactions.

Labs including blood counts, electrolytes, and kidney/liver function are completed by medical oncology every 1-2 weeks as standard of care for patients undergoing chemotherapy. The study team will use these laboratory results to monitor Adverse Events and subject safety. If platelet count qualifies as a Grade 3 toxicity as outlined in Appendix D, subjects will be discontinued from study drug. In the case of a grade 3 toxicity, this protocol will taper patients at a faster rate than usually recommended due to the risks associated with the thrombocytopenia (outlined in section 5.2).

13. **PR Interval Prolongation**

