4.3.1 Vulnerable Populations

Children, pregnant women, fetuses, neonates or prisoners are not included in this research study. Women of childbearing potential must be non-pregnant and non-lactating and willing to exercise an effective form of birth control during radiation therapy (e.g. oral contraceptive, IUD, condoms or other barrier methods etc.). Before receiving chemoradiation, female patients must have a negative pregnancy test. Hysterectomy or menopause must be clinically documented.

Early Withdrawal of Subjects

When to Withdraw Subjects

- 1. At the subject's request.
- 2. Determination by the investigator that it is no longer safe for the subject to continue therapy.
- 3. The presence of CTCAE Grade 4-5 toxicity possibly, probably or definitely related to the study drug.

How to Withdraw Subjects

1. If pregabalin has not been administered, the study subject will proceed to receive the recommended RT.

2. If pregabalin has been administered, the study subject will taper the dose gradually over a minimum of one week at the discretion of the treating physician/NP.

Data Collection and Follow-up for Withdrawn Subjects

Even though subjects may be withdrawn prematurely from the study, it is imperative to collect at least survival data on such subjects throughout the protocol defined follow-up period for that subject (though careful thought should be give to the full data set that should to be collected on such subjects to fully support the analysis). Such data is important to the integrity of the final study analysis since early withdrawal could be related to the safety profile of the study drug. If a subject withdraws consent to participate in the study:,

- If the patient withdraws consent, s/he will be given the choice of withdrawing completely meaning no further contact or data collection or giving the research team permission to follow up contact for data collection. It must be a high priority to try to obtain at least survivial data on all subjects. Patients that agree to be followed with be asked to sign to sign the 'Consent to Follow up' form (appendix G).
- If the PI, treating oncologist or physician withdraws the patient for any reason, the patient will be given the same choice as subjects who withdraw consent themselves. Patients agreeing to be followed with also sign the 'Consent to follow up.'

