1. Immediately removed from the study and discontinue the drug using the taper schedule outlined in section 8.1 (renal dose tapering).

2. Urgently referred to the counseling service at the Abramson Cancer Center.

3. Escorted to PEEC (Psychological Emergency Evaluation Center) if a patient reports suicidal thoughts and a plan to commit suicide that they intend to carry out.

Subjects who develop 1) grade 3 or GREATER thrombocytopenia; or 2) experience an unanticipated event (such as those outlined in the pregabalin package insert) will be directed to reduce their dose by 50% starting that day. The subject will then decrease the study drug by 1 pill per day thereafter until complete discontinuation. Patients titrating over the weekends will be directed to call the Radiation Oncologist on call if they experience any new side effects.

Approximately four weeks following completion of radiation treatments, study subjects will taper the pregabalin dose for a minimum of one week before stopping. This taper will follow a reverse schedule of the titration: 75mg twice daily for three days, 75mg once a day for three days, then no medication on the seventh day. The rate of taper may be modified by the PI or treating physician/NP as per the subject's clinical situation and PI or physician/NP's discretion.

Study subjects with persistent mucositis pain responding to pregabalin may continue to take the pregabalin for up to 4 additional weeks on study. After this point, any additional pregabalin administration will be off-study and solely at the discretion of the treating physician/NP. At that time, the cost of the medication will become the responsibility of the patient (or their medical insurance).

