7.5 Data Analyses

For each arm, the mean and standard deviation of the cumulative opioid dose will be computed. In addition, the number of patients who drop out prior to the end of the 11 week observation period will be noted. For each arm, the mean and standard deviation of the mucositis pain and quality of life scores will be computed at each time point. Descriptive analyses of the mean and SD of the cumulative opioid dose and the number of incomplete dropouts, will inform the design of a future randomized trial to test the hypothesis that Lyrica will significantly decrease the cumulative opioid dose over the 11 week observation period. No inferential analyses are intended in this study.

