7.6 Sample Size Justification

There is presently no data for head and neck patients. A total of 20 patients (10 per arm) will be sufficient to generate preliminary data on the primary and secondary endpoints. Study enrollment should be completed in 1 year. Follow-up will continue for an additional 2.5 months.

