7.7 Subject Populations for Analysis

We will analyze the all-treated population and any subject enrolled into the study that received at least one dose of study drug. Any patient who was randomized and then withdrew consent prior to receiving study drug will be replaced. The number of patients who drop out prior to the end of the 11 week observation period will be noted but these patients will be included in the analysis population.

8 Safety and Adverse Events

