(For example: A patient initiating LYRICA therapy for postherpetic neuralgia with normal renal function ($CLcr \ge 60$ mL/min), receives a total daily dose of 150 mg/day pregabalin. Therefore, a renal impaired patient with a CLcr of 50 mL/min would receive a total daily dose of 75 mg/day pregabalin administered in two or three divided doses.)

For patients undergoing hemodialysis, adjust the pregabalin daily dose based on renal function. In addition to the daily dose adjustment, administer a supplemental dose immediately following every 4-hour hemodialysis treatment (see Table 1).

Table 1. Pregabalin Dosage Adjustment Based on Renal Function Creatinine Clearance (CLcr) (mL/min)	Total Pregabalin Daily Dose (mg/day)*			Dose Regimen			
≥60	150	150 300 450 600 BID or TID					
30–60	75	150	225	300	BID or TID		
15–30	25-50	75	100-150	QD or BID			
<15	25	25-50	50-75	75	QD		
Sup	plementary	dosage fo	llowing hemo	odialysis (mg	z)†		
Patients on the 25 mg QD regimen: take one supplemental dose of 25 mg or 50 mg Patients on the 25–50 mg QD regimen: take one supplemental dose of 50 mg or 75 mg Patients on the 50–75 mg QD regimen: take one supplemental dose of 75 mg or 100 mg Patients on the 75 mg QD regimen: take one supplemental dose of 100 mg or 150 mg							

In this protocol, patients with a baseline GFR < 30 will be ineligible. Patients with GFR of 30-60ml/min (as determined by laboratory evaluation one week after chemotherapy and hydration) will have drug dose reduced to 75 mg, twice daily for the remainder of the study. Patients with a GFR < 30 will be removed from the study (also listed as exclusion criteria). Potential side effects associated with a quick taper far out weight the side effects of depression.

Hospitalization, Prolonged Hospitalization or Surgery

Any adverse event that results in hospitalization or prolonged hospitalization should be documented and reported as a serious adverse event unless specifically instructed otherwise in this protocol. Any condition responsible for surgery should be documented as an adverse event if the condition meets the criteria for and adverse event.

Neither the condition, hospitalization, prolonged hospitalization, nor surgery are reported as an adverse event in the following circumstances:

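### Several stopping rules take subjects off the study, not just off the drug, and nothing then secures their opioid diary to week 11, although they stay in the primary analysis

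*Combined protocol and SAP*

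**What the plan says.** Section 7.4 defines the primary quantity as opioid dose multiplied by days, summed over about 7 weeks of radiotherapy and 1 month afterwards. Section 3.4 takes it from a home diary that staff collect at visits.

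The rules for coming off treatment differ in what they end:

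- **Positive depression screen (5.2):** "Immediately removed from the study and discontinue the drug using the taper schedule".
- **Renal function (1.2.2 and 8.1):** "Patients with a GFR < 30 will be removed from the study".
- **Related grade 4-5 toxicity, or an investigator's judgement that therapy is no longer safe (4.3.1, early withdrawal):** listed as reasons to withdraw the subject.
- **Grade 3 platelets (1.2.3, item 12):** "subjects will be discontinued from study drug". Nothing is said about leaving the study.
- **Goal dose not reached or not held (5.2):** the subject may stay on study and is analysed.

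For withdrawn subjects, 4.3.1 says "it is imperative to collect at least survival data on such subjects throughout the protocol defined follow-up period for that subject". It adds in brackets that the full data set deserves thought, but does not define one. When the investigator or a physician withdraws the subject, "the patient will be given the same choice as subjects who withdraw consent themselves": either no further contact, or agreement to follow-up by signing the Consent to Follow up form (Appendix G). For subjects lost to follow-up, three documented attempts are made to confirm status.

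Section 7.7 says of those who drop out before week 11 that "these patients will be included in the analysis population". Section 7.5 will use the mean and SD of cumulative opioid dose and the number of dropouts to plan the next trial.

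**The concern.** The one item called imperative after withdrawal, survival, is not an objective or endpoint in Sections 2, 3 or 7. The item that the trial exists to measure is not required. A subject removed in week 4 may go on attending radiotherapy and taking opioids while the plan asks for no further record of the dose. The subject still counts in the 11-week mean.

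All three planning outputs are exposed. A truncated total pulls the mean down and changes the SD. The dropout count mixes subjects who left with subjects whom a rule removed but who might have kept a diary. Section 4.3.1 itself concedes that early withdrawal may be related to the drug's safety profile, so the missing weeks cannot be presumed unrelated to treatment. Weeks that were never recorded cannot be recovered at analysis.

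There is also an internal tension. Section 8.1 sets adverse event reporting to 30 days after the last dose and asks that unresolved events be followed. Section 4.3.1 offers an end to all contact to subjects who did not withdraw consent.

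**Working it through.** **Inputs from the documents.** 10 subjects per arm (7.6) and 7 + 4 weeks (7.2). The plan's totals reproduce: 10 + 10 = 20 subjects, 7 + 4 = 11 weeks. The documents give no removal rate, no SD and no weekly opioid profile, so those are assumed below.

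**Step 1: weeks not collected.** If recording stops at the end of week w, the uncollected share is (11 - w)/11.

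- w = 2: 9/11 = 82%
- w = 4: 7/11 = 64%
- w = 6: 5/11 = 45%

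**Step 2: share of the dose captured, s.** Two assumed profiles:

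- Flat use: s = w/11.
- Rising use: weekly weights 0, 0, 1, 2, 3, 4, 5, 5, 4, 3, 2 (sum 29). The weights are assumed. Section 1.1.4 supports a rise, citing analgesic use going from 34% at baseline to 80% at week 6.

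**Step 3: effect on an arm mean.** Section 7.5 has no rule for a truncated total, so assume the partial sum is used as the total. Assume also that removed subjects would otherwise have had the arm's average dose. With k of 10 removed, the mean is understated by (k/10) × (1 - s).

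| Removal after week | s, flat | s, rising | k = 1 | k = 2 | k = 3 |
|---|---|---|---|---|---|
| 2 | 2/11 = 18% | 0/29 = 0% | 8.2-10% | 16-20% | 25-30% |
| 4 | 4/11 = 36% | 3/29 = 10% | 6.4-9.0% | 13-18% | 19-27% |
| 6 | 6/11 = 55% | 10/29 = 34% | 4.5-6.6% | 9.1-13% | 14-20% |

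In each cell the first figure is flat use and the second is rising use. For example, k = 2 at week 4 gives 0.2 × 7/11 = 12.7% and 0.2 × 26/29 = 17.9%.

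**Step 4: effect on the SD.** Scale the true mean to 1, let c be the coefficient of variation and p = k/10. Then the observed mean is m = 1 - p(1 - s), the observed variance is (1 + c²)(1 - p + p·s²) - m², and the SD ratio is its square root divided by c. For k = 2 and s = 0.36, m = 0.872 and the ratio is 1.25, 1.04 or 0.96 for c = 0.3, 0.5 or 0.8. Over k = 1 to 3, s = 0.09 or 0.36 and the same three c values, it runs from 0.93 to 1.62. The SD can move either way.

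**Step 5: imbalance.** With no true effect, 2 removals after week 4 on pregabalin and none on placebo would show as an opioid reduction of 13% to 18%. The reverse split would hide a benefit of that order.

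**Step 6: would it arise at all?** At an assumed removal risk per subject of 5%, 10% or 20%, the chance of at least one removal among 20 is 1 - (1 - risk)^20 = 64%, 88% or 99%.

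**The case against.** The strongest reply is that 4.3.1 sets a floor, not a ceiling. Every withdrawn subject is offered follow-up, data up to removal are kept, and dropouts are analysed. The Consent to Follow up form may define what is collected; its text is not in the documents as available. All of this stands. A reader might infer that the primary endpoint is lost after removal. The text does not support that. It supports only that nothing requires the endpoint to be collected.

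A reader might also infer that the removed subjects are those most likely to differ between arms. The documents do not show it. The large cited differences, dizziness (31% against 9%) and somnolence (22% against 7%), are in 1.2.3, and 5.2 lets subjects with sedation or dizziness delay escalation or reduce the dose and stay on study. The cited by-arm figure closest to a removal rule is suicidal behaviour or ideation, 0.43% against 0.24%. None is given for GFR below 30 or for the depression score. Nor can a number of removals be derived from the screening schedule, because no rate of positive screens is stated.

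It is also too broad to say that the protocol always equates stopping drug with leaving the study: the platelet rule and the dose-limitation rule do not.

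Finally, this is a small pilot, and "No inferential analyses are intended in this study". That removes any concern about a test result. It does not protect the mean, SD and dropout count, which are what the pilot delivers. Attrition under the protocol's own rules is worth measuring, but one count cannot separate stopping drug from loss of the endpoint.

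**Conclusion.** The point holds in this form: under several rules the subject leaves the study, survival is then the only required item, and the diary-based primary endpoint is not secured to week 11 for subjects whom 7.7 keeps in the analysis. The uncollected time is simple arithmetic: 82%, 64% or 45% of the window for removal after week 2, 4 or 6.

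The effect on the results is conditional. With 1 to 3 of 10 subjects removed after weeks 2 to 6, the arm mean would be understated by 4.5% to 30%. This rests on the assumed profiles, on partial sums being used as totals, on removed subjects being average opioid users and on nobody opting in to follow-up. Opt-in would shrink it. Removals balanced between arms would still distort the mean and SD; any imbalance would also appear as a treatment difference. Whether one would occur, and in which direction, the documents do not say.

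**What to change.** - **4.3.1:** Separate discontinuation of study drug from withdrawal from the study. State that subjects who come off study drug under any rule continue the opioid/pain diary, OMQ, BPI, QLQ-C30 and adverse event collection through the 11-week window, at the routine visits, unless they decline. Put this data set in place of the survival-only minimum.
- **Consent:** Cover the continued collection in the main consent, and limit the Consent to Follow up form to subjects who themselves withdraw consent.
- **Lost to follow-up:** Have the three contact attempts also ask for the diary.
- **7.5:** Report drug discontinuation and loss of opioid data as two separate counts by arm, with reason and week.
- **1.2.2, 1.2.3, 5.2 and 8.1:** Leave the clinical triggers and the stopping and taper wording unchanged. The sponsor must reconcile where these sections speak of removal from the study and where of discontinuation of study drug.

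The sample size stays at 20. If collection continues to week 11 the truncation disappears, except for subjects who decline or cannot be reached. The cost is protocol and consent wording and a small questionnaire burden for off-drug subjects, who may decline. No visits are added: Sections 6.3 and 6.4 describe the weekly on-treatment visit and the one-month visit as routine.

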5.1 Description

Pregabalin is an agent with anti-nociceptive and anti-seizure effects believed to exert its effect through binding to the $\alpha 2$ - δ subunit of voltage-gated calcium channels in the central nervous system. It is available as hard-shelled capsules containing 25, 50, 75, 100, 150, 200, 225, and 300 mg of pregabalin and as oral solution containing 20 mg/mL. The solution is clear and colorless contained in a 16 fluid ounce white HDPE bottle.

5.2 Treatment Regimen

Study subjects will self-administer oral preparation of pregabalin or matching placebo in twice daily dosage. Study subjects may use capsule form or solution, depending on medical necessity.

All study subjects will start taking 75mg of pregabalin nightly starting on the first day of radiation treatments. The dose will be increased to 75mg twice daily on day 3 and subsequently to 150mg twice daily on day 5.

Study subjects randomized to the treatment arm will continue to take 150mg of pregabalin twice daily for the duration of their radiation treatments until approximately their one month follow up visit. Subjects will be instructed at their follow up visit on how to taper the study drug.

Subjects randomized to the placebo arm will receive capsules and/or liquid that looks identical to the treatment arm. Subjects will titrate and taper in a fashion identical to the treatment arm.

At the discretion of the treating physician/NP, the interval between increasing dosage may be prolonged to a maximum of 4 days or the dosage reduced after the goal dose has been reached. Participants reporting excessive sedation or dizziness will be allowed to delay dose escalation. If a patient is not able to reach or maintain the goal dose at any point during the study (such as due to an adverse event at least possibly related to the study drug), the patient may continue on study and will be included in the analyses. The dose reached/dose

CONFIDENTIAL

Page 14

reduction will be recorded by the treating physician/NP with annotation of the rationale for the decision to maintain at that dose.

During titration, patients will be assessed daily by designated study staff before or after their daily radiation treatment in order to discuss/report with/to the PI any adverse events associated with the study drug.

Patients will be screened for suicidal ideation by designated study staff at baseline, daily during week 1 titration of the study drug and on a weekly basis during the study period until chemotherapy and radiation therapy are completed. Patients will be screened for depression again at the 1 month inspection visit. All patients will be screened using the Depression Screening assessment (appendix H).

Patients scoring a 10 or higher or reporting anything other than a 0 on question # 5 will meet with a physician/NP and will be:

1. Immediately removed from the study and discontinue the drug using the taper schedule outlined in section 8.1 (renal dose tapering).

2. Urgently referred to the counseling service at the Abramson Cancer Center.

3. Escorted to PEEC (Psychological Emergency Evaluation Center) if a patient reports suicidal thoughts and a plan to commit suicide that they intend to carry out.

Subjects who develop 1) grade 3 or GREATER thrombocytopenia; or 2) experience an unanticipated event (such as those outlined in the pregabalin package insert) will be directed to reduce their dose by 50% starting that day. The subject will then decrease the study drug by 1 pill per day thereafter until complete discontinuation. Patients titrating over the weekends will be directed to call the Radiation Oncologist on call if they experience any new side effects.

Approximately four weeks following completion of radiation treatments, study subjects will taper the pregabalin dose for a minimum of one week before stopping. This taper will follow a reverse schedule of the titration: 75mg twice daily for three days, 75mg once a day for three days, then no medication on the seventh day. The rate of taper may be modified by the PI or treating physician/NP as per the subject's clinical situation and PI or physician/NP's discretion.

Study subjects with persistent mucositis pain responding to pregabalin may continue to take the pregabalin for up to 4 additional weeks on study. After this point, any additional pregabalin administration will be off-study and solely at the discretion of the treating physician/NP. At that time, the cost of the medication will become the responsibility of the patient (or their medical insurance).

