DSMC - Data Safety and Monitoring Committee

DOCM - Department of Compliance and Monitoring

Title	A Pilot Study at a Single-Institution of Pregabalin in the Management of Mucositis Pain in Patients undergoing Chemoradiation Therapy to the Head and Neck.
Short Title	Lyrica Study
Protocol Number	IRB 819266; UPCC 43313
Phase	Pilot
Methodology	Prospective, randomized
Study Duration	18 months
Study Center(s)	Single-center
Objectives	To assess the efficacy of Pregabalin in the management of mucositis pain in patients receiving radiotherapy to the head and neck.
Number of Subjects	20
Diagnosis and Main Inclusion Criteria	Adult patients undergoing photon or proton radiation therapy and concurrent platinum-based chemotherapy for head and neck cancer.
Study Product, Dose, Route, Regimen	Pregabalin (Lyrica) oral administration with dose of 150mg twice daily vs. placebo
Duration of administration	Approximately 10-12 weeks
Reference therapy	n/a
Statistical Methodology	This is a 2 arm double blind randomized pilot trial to generate preliminary data on the cumulative opioid dose for head and neck cancer patients treated with either placebo (the control arm) or Lyrica (pregabalin). Ten patients will be enrolled on each arm for a study total of 20 patients. The primary objective is to generate preliminary data on the cumulative opioid dose over the 11 week observation period for head and neck cancer patients treated with either placebo (the control arm) or Lyrica. For each arm, the mean and standard deviation of the cumulative opioid dose will be computed. In addition, the number of patients who drop out prior to the end of the 11 week observation period will be noted. The mean and SD of the cumulative opioid dose and the number of incomplete dropouts, will inform the design of a future randomized trial to test the hypothesis that Lyrica will significantly decrease the cumulative opioid dose over the 11 week observation period. No inferential analyses are intended in this study.

Study Summary

1 Introduction

This document is a protocol for a human research study. This study is to be conducted according to US and international standards of Good Clinical Practice (FDA Title 21 part 312 and International Conference on

Version 06-01-2015 Page 2 Harmonization guidelines), applicable government regulations and Institutional research policies and procedures.

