6.3 On Treatment Visits

Subjects will be instructed to begin taking the study drug on the first day of radiation treatment (or if applicable – on a day following the first radiation treatment up through the end of the 2^{nd} week of radiation treatment). On a weekly basis, the subject will be provided with an adequate supply of study drug and will be given instructions on details of administration in accordance with the assigned study cohort and treatment regimen (see Sections 3.1 and 5.2).

During each routine weekly on treatment visit (or another day weekly while on treatment), the subject will complete the validated oral mucositis questionnaire (OMQ) (see Appendix F), the pain assessment, the Depression Screening and the quality of life questionnaire. In addition, the pain diary and the pill diary will be collected from the patient for the corresponding week. The physician/NP or designee will complete the toxicity assessment form with the subject. If subjects require additional on treatment visits in addition to the routine weekly visit, no study documentation is required unless there is an adverse event, in which case the appropriate procedure will be followed as outlined in Section 8.

During titration, patients will be screened daily by designated study staff before or after their daily radiation treatment in order to discuss/report with/to the PI any potential adverse events associated with the study drug. In addition, during titration patients will be screened for suicidal ideation by designated study staff before or after their daily radiation treatment. All patients will be screened using the Depression Screening assessment (appendix H). For patients scoring a 10 or higher or reporting anything other than a 0 on question # 5, the procedure outlined in Section 5.2 will be followed.

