7.2 Design

This is a 2 arm *double blind* randomized pilot trial to generate preliminary data on the cumulative opioid dose for head and neck cancer patients treated with either placebo (the control arm) or Lyrica (pregabalin). To reduce bias in terms of initiation of opioid treatment and dosage prescribed, neither the patient, the study coordinator, nor the treating physician/nurse practitioner will know whether Lyrica or placebo had been assigned to a patient. The cumulative opioid dose over an 11 week observation period will be recorded. Randomization will eliminate selection bias and balance patient factors between arms. Ten patients will be enrolled on each arm for a study total of 20 patients. Study drug will be taken daily during the approximately 7 weeks of radiotherapy and for 4 additional weeks post-radiotherapy. The primary choice of the opioid drug for this study is oxycodone.

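### Weekly suicidality screening stops with chemoradiation while study drug continues, leaving about 3 weekly screens unscheduled before the one-month visit and none in any extension

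*Combined protocol and SAP*

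**What the plan says.** **Screening.** Under Section 5.2, Appendix H is given at baseline, daily in the first week of titration, and then "on a weekly basis during the study period until chemotherapy and radiation therapy are completed". One more screen follows at the one-month visit. Section 6.3 places the weekly form at clinic visits: "During each routine weekly on treatment visit (or another day weekly while on treatment". The Section 6.5 schedule has columns for baseline, weekly on-treatment visits and the follow-up visit. It has none between the last two and none after follow-up.

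**Drug.** Section 5.2 continues 150 mg twice daily "for the duration of their radiation treatments until approximately their one month follow up visit". Section 7.2 says: "Study drug will be taken daily during the approximately 7 weeks of radiotherapy and for 4 additional weeks post-radiotherapy". The Study Summary gives the duration of administration as "Approximately 10-12 weeks". About four weeks after radiotherapy, "study subjects will taper the pregabalin dose for a minimum of one week before stopping". Patients whose mucositis pain persists and is responding "may continue to take the pregabalin for up to 4 additional weeks on study". Section 6.4 allows the follow-up visit from 3 to 6 weeks after radiotherapy.

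**Action on a positive screen.** A score of 10 or more, or any non-zero answer to question 5, leads to a meeting with the physician or nurse practitioner. The patient is then "Immediately removed from the study and discontinue the drug" by taper and urgently referred to counseling. A patient with a plan and intent is escorted to the psychiatric emergency center.

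**The concern.** Section 1.2.3 presents suicidal thoughts and behavior as a risk of antiepileptic drugs. It calls for patients on any of them to be monitored, and reports that the risk appeared within a week and lasted as long as treatment was studied. Section 8.1 ties adverse event reporting to the last dose. Section 5.2 instead ties the active screen to chemoradiation, which is not the source of the risk being screened for, and gives no reason for that stop point.

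At stake is how late a serious event might be found. If suicidal thoughts begin in the weeks after radiotherapy, detection depends on the patient, the family or a chance contact until the one-month visit. For a patient who takes the extension, it depends on them again afterwards. The daily contact that radiotherapy brings has also ended by then.

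**Working it through.** **Inputs.** Radiotherapy about 7 weeks and post-radiotherapy dosing 4 weeks (Section 7.2). Visit window 3 to 6 weeks (Section 6.4). Taper and extension (Section 5.2). Weekly interval (Section 5.2, during chemoradiation). Excess risk by indication (Section 1.2.3, Table 2).

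**The plan's own figure.** The plan states no number of screens. It does state an 11-week period: 7 + 4 = 11, which reproduces. Adding a one-week taper gives 12, the top of the Study Summary range.

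**Screens absent before the visit.** If the weekly interval continued after radiotherapy, a visit in week *v* would be the *v*th screen. Only the visit screen is scheduled, so the number absent is *v* − 1.

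| Visit, weeks after radiotherapy | Weekly screens due, including the visit | Scheduled | Absent |
|---|---|---|---|
| 3 | 3 | 1 | 2 |
| 4 (nominal) | 4 | 1 | 3 |
| 6 | 6 | 1 | 5 |

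The last row needs full dosing to run to a 6-week visit. That would be 7 + 6 = 13 weeks on drug, beyond the Study Summary range, and Section 5.2 also starts the taper at about four weeks. So 5 is a conditional upper limit.

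Nominally, 3 of 11 drug weeks is 27%. Sections 3.1 and 6.3 let drug start as late as the end of radiotherapy week 2, giving 3 of 9, or 33%. The count is steadier than the percentage.

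**Taper.** The standard schedule is three days of 75 mg twice daily, three days of 75 mg once daily, and no drug on day 7. If it starts at the visit, where the patient is screened, the next weekly screen falls after the last dose. Extra screens needed: 0. A taper of more than one week, which Section 5.2 permits, would need more.

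**Extension.** Up to 4 weeks at one screen a week is up to 4 screens, with 0 scheduled. The order of extension and taper is not stated; I assume the extension comes first. A patient with a 4-week visit and the full extension then has up to 3 + 4 = 7 absent.

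**Size of the risk.** Table 2 gives an excess of 0.9 per 1000 for indications other than epilepsy and psychiatric illness.

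- Over the course, in 10 pregabalin patients: 10 × 0.0009 = 0.009 cases.
- In the 4 post-radiotherapy weeks, if the excess is spread evenly over 11 weeks (an assumption): 0.009 × 4/11 ≈ 0.003.
- With the table's highest row instead (psychiatric, 2.9 per 1000): 10 × 0.0029 = 0.029.

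Section 4.2 excludes serious mood disorder, attempted suicide and positive screens at entry, so the true excess may be lower. The background rate in these patients, which a screen would also pick up, is not given.

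**The case against.** The strongest reply is that screening frequency is a design choice. Sections 5.2, 6.3, 6.4 and 6.5 agree with one another, and Section 1.2.3 calls for monitoring without naming an interval. This stands. A reader might infer that the plan contradicts itself or that required screens are being skipped. Neither is so: the screens are absent only relative to the weekly interval that the plan uses during chemoradiation.

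Second, other cover exists. Patients are told to report worrying thoughts at once, and families are to be alerted (Section 1.2.3). Adverse event reporting runs to 30 days after the last dose (Section 8.1). Providers must ask about adverse events at each contact (Section 8.2), and the toxicity form grades suicidal ideation. So a reader should not infer that patients are unmonitored after radiotherapy. But this cover is passive or needs a contact, and none is scheduled before the visit. After radiotherapy the toxicity form is due only at that same visit.

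Third, more screening could remove more patients from a 20-patient pilot that reports dropouts. That is a fair cost. The documents give no positive-screen rate, so its size cannot be estimated. Section 7.7 keeps dropouts in the analysis population, and the rule is the same in both blinded arms.

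Fourth, the pathway after a positive screen has a loose end. Section 5.2 sends the taper to Section 8.1, which holds a renal dose-adjustment table and not a taper schedule. That is true, but it already affects screens during radiotherapy and is no reason to stop screening early.

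**Conclusion.** The concern holds as a safety-monitoring gap. The active screen is tied to chemoradiation although the risk belongs to the drug. About 3 weekly screens are unscheduled before a 4-week visit (2 to 5 across the window, if full dosing runs to the visit), up to 4 more in a full extension, and some in any taper longer than a week.

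Two stronger readings are tempting. One is that the ordinary taper adds a fourth absent screen for every patient. The drug-free seventh day means it may not. The other is that the gap damages the trial's results. It does not affect the sample size, the endpoint definition or the descriptive analysis.

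The expected excess, about 0.009 cases in 10 pregabalin patients, is very small. The case rests on the severity of the event, the protocol's own account of how long the risk lasts, and the low cost of closing the gap. The counts assume a weekly interval and drug taken up to the visit.

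**What to change.** **Stop point.** In Sections 5.2, 6.3 and 6.5, require Appendix H weekly until the last dose of study drug, including the post-radiotherapy weeks, any extension and any taper longer than one week. After radiotherapy the same designated staff give it by telephone or at any clinic contact. Confirm first that the form suits telephone use; if not, the patient can complete a paper copy at home and read out the answers.

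**Remote response.** Add a short step to Section 5.2, because the escort step presumes the patient is on site. Confirm the patient's location at the start of each call. A positive screen gets same-day contact from the physician or nurse practitioner and urgent in-person assessment. A patient with a plan and intent goes to emergency psychiatric services while staff stay on the line. The trigger is unchanged.

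**Reporting.** In Section 7.5, count screen-triggered removals separately within the dropouts so that the figure remains usable for planning the next trial. No new consent is needed: the early-withdrawal section already offers withdrawn patients continued data collection.

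**Cost.** Nominally 3 calls per patient: 3 × 20 = 60 calls, and at an assumed 10 minutes each 600 minutes, or 10 staff hours. Across the visit window this is 40 to 100 calls, or about 7 to 17 hours. If every patient took the full extension after a 4-week visit, it would be 7 × 20 = 140 calls, about 23 hours. Add physician or nurse practitioner time for positives, and possibly a few added or earlier removals whose number the documents do not allow one to estimate.

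A lighter option is a screen at the extension decision plus a stated reason for ending weekly screening with radiotherapy. It would leave the weeks before the visit uncovered.
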